### 10.2 Training of Staff

A formal meeting (Investigator’s meeting) will be conducted prior to site initiation. During this meeting, the Sponsor or its authorized representative will discuss the requirements of the clinical study protocol and related documents and will also provide training to the relevant systems and other study-specific procedures. The activities of this meeting will be described in the monitoring plan.

#### Confidentiality Statement

Data and information contained in this document are considered to constitute trade secrets and confidential commercial information, and the legal protections provided to such trade secrets and confidential information are hereby claimed under the provisions of applicable law. No part of this document may be publicly disclosed without the written consent of Philip Morris Products S.A.

Further to the Investigator's meeting, the Investigator or designee will ensure that appropriate training relevant to the study is regularly provided to all staff involved in the study, and that any new information relevant to the performance of this study is forwarded in a timely manner to the staff. The Investigator or designee will maintain a record of all individuals involved in the study.

The Monitor will also train the site staff on study procedures during the site initiation visit, and this training will be documented.

### **10.3 Audits and Inspections**

Good Clinical Practice regulations require independent inspections of clinical program activities. Such inspections may be performed at any time before, during and/or after the study.

Authorized representatives of the Sponsor, regulatory agencies and/or IEC may perform audits or inspections, including source data verification. The purpose of an audit or inspection is to systematically and independently examine all study-related activities and documents to determine whether these activities were conducted and data was recorded, analyzed and accurately reported according to the protocol, ICH GCP guidelines and any applicable regulatory requirements. The Investigator or designee will contact the Sponsor or the authorized representative immediately if contacted by a regulatory agency about an inspection at their investigational site.

The Investigator and study staff are responsible for maintaining a comprehensive and accurate filing system of all study-related documentation that will be suitable for inspection at any time by the Sponsor, its authorized representative and/or regulatory agencies. By signing this protocol, the Investigator or designee understands and agrees to provide access to the necessary documentation and files.

## 11 DATA MANAGEMENT ACTIVITIES

All data management activities will be described in detail in the data management plan (DMP) and referenced documents. The electronic systems used to collect subject data, CRF and electronic patient reported outcome (ePRO), will be FDA 21 CFR Part 11 compliant.

### 11.1 Data Capture

#### 11.1.1 Case Report Forms and Study Records

With the exception of the subject-reported outcome data, all results from the clinical assessments will be recorded in the source documents by the Investigator or their authorized designee(s) and then captured in the CRFs at the investigational site. The subject questionnaires and the daily product use (P3P, cigarettes, e-cigarettes or other) will be entered by the subject directly in a diary. Trained study personnel will be responsible for capturing the data from the observations, tests and assessments specified in the protocol in the source documents and then transferring the data into the CRF, in accordance with the CRF Completion Guidelines.

The Investigator has ultimate responsibility for the collection and reporting of all data related to the clinical study and ensuring that the data are accurate, authentic/original, legible, timely (contemporaneous), enduring and available when required. The CRF must be signed by the Investigator to attest that the data contained in the CRF are true and accurate. Any corrections made to source documents must be clearly recorded, without obscuring the original values and be accompanied by the date of change, reason for change and identification of the person making the change. The CRF for each subject will be checked against the source documents at the investigational site by the Monitor. Instances of missing or unclear data will be discussed with the Investigator for resolution. All subject reported outcome questionnaires including instructions will be provided in the subject's local language, and transcribed in the CRF in English. A CRF will be generated for all subjects who have signed the ICF.

#### 11.1.2 Protocol Deviations

Protocol deviations are defined as any deviations from the procedures defined in this document, including but not limited to, any violation of inclusion/exclusion criteria, assessments not performed or performed outside the scheduled time windows, or use of drugs that are known to affect study endpoints.

Protocol deviations will be entered into the clinical trial management system (CTMS) or other approved format. The data collected in the CRF will be used to assess protocol deviations from the data programmatically. Protocol deviations will be reconciled prior to closing the study and locking the clinical database.

#### Confidentiality Statement

Data and information contained in this document are considered to constitute trade secrets and confidential commercial information, and the legal protections provided to such trade secrets and confidential information are hereby claimed under the provisions of applicable law. No part of this document may be publicly disclosed without the written consent of Philip Morris Products S.A.

Information from the source documents will represent the primary source of protocol deviations. Information following investigational site monitoring and other manual reviews will be documented in the investigational site visit reports, follow-up letters, audit documentation, or other manual review and will be recorded and tracked in the CTMS or other approved format. Telecommunications and other verbal communications regarding deviations will be considered and handled as important communication, documented and tracked as protocol deviations, as necessary.

Individual entries for protocol deviations that are recorded in the CTMS, or other approved format, following investigational site monitoring and other manual reviews, will be reviewed against the individual data points in the CRF database. The overall procedure for managing protocol deviations are defined in the SOPs and study specific procedures of the CRO. All deviations will be reviewed, as determined at study start, to identify trends to improve monitoring and/or potential impact on the statistical analysis.

## 11.2 Data Handling

All study data will be managed by the data management team at the CRO responsible for this study. The overall procedures for quality assurance of clinical study data are described in the SOPs of the CRO. The CRO will prepare the DMP that will be approved by the Sponsor, prior to the start of the study. This document will describe, in detail, the procedures and processes related to data management.

Data of all subjects that sign the ICF will be captured and stored in the study database. For Screen Failures the following information should be captured: date/time of ICF signature, date of birth, sex, race, AEs, concomitant medication given for treatment of AEs, date and reason for screen failure.

All data collected during the study is property of the Sponsor, irrespective of the location of the database and the CRO.

Additional details are covered in the DMP.

### 11.2.1 Data Verification

The data will be verified as defined in the DMP and data validation plan (DVP). Discrepancy will be generated electronically, and queries will be issued to the investigational site, as necessary.

Data queries will be raised for discrepant or missing data. All changes to data will be captured in the database with a comprehensive audit trail.

### 11.2.2 Coding

Adverse events, concomitant diseases, medical/surgical history, prior/concomitant medication will be classified according to the terminology of the latest version of the following dictionaries, at time of coding the first entry:

Adverse events, concomitant disease, medical/surgical history: Medical Dictionary for Regulatory Activities (MedDRA®)

Prior/concomitant medications: WHO Drug Dictionary Enhanced and Anatomical Therapeutic and Chemical classification system

### 11.2.3 Database Lock

When all outstanding data management issues have been resolved and quality review and cleaning activities are complete, the database or selected data is/are declared soft-locked. Access to change data in the soft-locked database or to change selected data at this time is limited.

After data review by the Sponsor, resolution of all raised queries and quality control of the changed data, the database or selected data thereof will be declared locked upon Sponsor approval, as applicable.

Any changes to the database after that time can only be made by written agreement between the Sponsor and the data management and statistical team at the CRO. Any of those changes must be documented in the database log file.

The study database will be transformed into a Clinical Data Interchange Standards Consortium (CDISC) compliant format and transferred to the Sponsor as specified in the DMP and defined in the data transfer agreement. The clinical data will adhere to the CDISC Study Data Tabulation Model Data Structure Specifications.

## 12 PLANNED STATISTICAL METHODS

### 12.1 General Considerations

Full details of the statistical analysis will be given in the statistical analysis plan (SAP). The following statistical analyses will not be performed prior to the finalization of the SAP. Any changes to the planned statistical methods from the SAP will be documented in the research study report (RSR). The statistical evaluation will be performed using SAS®, version 9.2 or later.

#### 12.1.1 Stratification Criteria

The sample randomization will enforce at least 40% of each sex in each product variant. Analyses stratified by sex will be detailed in the SAP.

#### 12.1.2 Definitions for Statistical Data Analysis

For plasma nicotine time-concentration and VAS-craving, baseline will be defined as the last measurement prior to product use for PK assessment (prior to T0)

For the changes from baseline in PK parameters, PD parameters, CYP2A6 and product acceptance, described in sections 3.1 and 3.2, Day 1 value will be considered as the baseline. For BoExp and safety parameters the last assessments prior to product test will be considered as baseline.

#### 12.1.3 Descriptive Statistics

All data will be presented in listings.

All endpoints will be summarized with descriptive statistics including number of subjects (n), number and percent of subjects with missing data, arithmetic means, 95% confidence intervals of the mean, and standard deviations (mean and SD), median, first and third quartiles, minimum and maximum. Change from baseline will be added to the summary statistics when applicable.

For log-normally distributed endpoints geometric mean, 95% confidence intervals of the geometric mean, geometric CV will be presented instead of arithmetic mean, 95% confidence intervals of the mean, and SD and percent change from baseline will be presented instead of change from baseline.

Categorical variables will be summarized by frequency statistics (number and percentage).

For endpoints relating to sampling times (e.g., tmax) only median, first and third quartiles, and minimum and maximum will be presented.

#### 12.1.4 Handling of Missing Values and of Values outside the Detection Limits

In general, missing data will not be imputed.

For questionnaire data total scores and domain or subscale scores a certain degree of imputation may occur by averaging across individual item scores. Further details will be provided in the SAP.

For biological measurements, values below the lower limit of quantification (LLOQ) will be imputed using  $0.5 \times$  lower limit of quantification. For values above the upper limit of quantification (ULOQ), i.e., preceded by a “>”, for example “>xx,” the numerical xx will be used for calculation and reporting in summary tables. The number and percent of values below LLOQ or above ULOQ will be presented in each summary table.

#### 12.1.5 Significance Level for Inferential Analysis

Not applicable.

### 12.2 Determination of Sample Size and Power Consideration

A total of 60 subjects will be enrolled randomized with a 1:1 randomization ratio (~30 subjects randomized to P3P-1mg and ~30 to P3P-2mg). The sample size is empirically based.

### 12.3 Analysis Populations

Pharmacokinetic, pharmacodynamics, product acceptance, puffing/inhalation behavior endpoints will be analyzed using the PK population by actual product exposure and overall. Nicotine/tobacco containing product use, tobacco and nicotine containing product dependence, and CYP2A6 activity will be analyzed using the randomized population by actual product exposure and overall. Exposure to harmful and potentially harmful constituents will be analyzed using the randomized population. Safety will be analyzed using the safety population by actual product exposure and overall.

Actual product use exposure categories will be further defined in the SAP. Additional populations for sensitivity analysis could be defined in the SAP.

#### 12.3.1 Safety Population

The safety set population, consists of all the subjects who give informed consent, have at least one exposure to P3P (including the product test at Admission [Day -1]) and have at least one safety assessment.

#### 12.3.2 Randomized population

The randomized population is a subset of the safety population and consists of all randomized subjects who had at least one post-randomization P3P use experience and have at least one valid non-safety assessment.

### 12.3.3 Pharmacokinetic Population

The PK population is a subset of the randomized population and consists of all subjects who completed at least one of the single use of P3P for PK assessment, and for whom at least one primary nicotine PK parameter can be derived. Only subjects without major protocol deviations, as defined in the SAP, which have an impact on evaluability of the primary objective will be included in the PK population.

Additional analysis sets may be defined in the SAP.

## 12.4 Demographics and Baseline Characteristics

Demographic information and baseline characteristics will be summarized for the safety population, randomized population, and PK population.

Summaries will include sex, age, height, weight and BMI, smoking history, ABOUT Dependence Questionnaire, CYP2A6 activity and other endpoints that are only captured prior to product use.

These data will be summarized as described in section [12.1.3](#).

## 12.5 Primary Objective and Endpoints

### 12.5.1 Primary Endpoint Analysis Variables

PK endpoints are listed in section [3.1](#).

Nicotine PK parameters will be derived from plasma nicotine concentration versus time data.  $AUC_{(0-4h)}$  will be derived using the trapezoidal method.

To minimize the carry-over effect in the nicotine plasma PK parameters due to limited washout periods (see section [4.2](#)), background-concentration correction will be applied to the nicotine concentration data.

Baseline nicotine concentration ( $C_0$ ) will be defined as the last measured concentration prior to  $T_0$  of each visit. The baseline correction will be implemented by calculating the PK parameters using adjusted concentration values as described below [\(1\)](#):

- Calculate the slope using a linear regression on the log concentration of the 3 pre-  $T_0$  timepoints.
- If the slope is  $\leq 0$ , then use the slope to determine the elimination rate constant  $\lambda_z$ .
- If the slope is  $> 0$ , then use the average (geometric mean) of the subject's slopes that are  $\leq 0$  from the other visits to determine  $\lambda_z$ . If the subject's slopes are positive for all of the visits, baseline corrected PK parameters will not be calculated.
- Adjust each concentration value post-baseline using the following formula:

---

#### Confidentiality Statement

Data and information contained in this document are considered to constitute trade secrets and confidential commercial information, and the legal protections provided to such trade secrets and confidential information are hereby claimed under the provisions of applicable law. No part of this document may be publicly disclosed without the written consent of Philip Morris Products S.A.

---

$$cC_t = C_t - C_0 * e^{-\lambda z t}.$$

$cC_t$  is the corrected concentration at each time point,  $C_t$  is the concentration at each time point,  $C_0$  is the pre-use baseline nicotine concentration,  $\lambda_z$  is the elimination rate constant and  $t$  is the actual time.

The following PK parameters will be derived from nicotine levels adjusted for baseline:

$cC_{max}$  Background-corrected maximum observed plasma concentration.  $cC_{max}$  will be reported as long as there is at least one quantifiable concentration post-exposure

$ct_{max}$  Time to maximum concentration  $cC_{max}$

$cAUC_{(0-4h)}$  Background-corrected area under the plasma concentration-time curve from start of product use ( $T_0$ ) to 4 hour

Unadjusted PK parameters will also be presented.

More details on nicotine PK parameter derivations will be provided in the SAP.

### 12.5.2 Baseline Comparability

Not applicable.

### 12.5.3 Statistical Analysis

PK parameters will be summarized as described in section 12.1.3.

Nicotine PK profiles will be summarized and plotted over time for each visit.

An analysis of variance (ANOVA) will be conducted for Day 1 and Day 30 on background-corrected  $AUC_{(0-4h)}$  and background-corrected  $C_{max}$  endpoints in the natural logarithmic scale. The model will include sex as a covariate. The results of this analysis for each of  $cAUC_{(0-4h)}$  and  $cC_{max}$  will be presented as geometric least square means and 95% confidence intervals for each variant and least square mean ratio and 95% confidence intervals of P3P-2mg:P3P-1mg ratio.

For the ANOVA tests, the following hypothesis will be tested:

$H_0: \mu_1 = \mu_2$

$H_1: \mu_1 \neq \mu_2$

where  $\mu_1$  and  $\mu_2$  are the means (arithmetic or geometric) for each product variant, respectively.

## 12.6 Secondary Objectives and Endpoints

### 12.6.1 Secondary Endpoint Analysis Variables

#### 12.6.1.1 PD endpoints

PD endpoints are listed in section [3.2](#).

VAS craving score and changes from baseline will be summarized by timepoint. In addition, AUCVAS will be derived by P3P variant: AUCVAS (0-4h).

Sensory Questionnaire and ABOUT Product Experience Questionnaire will be described as detailed in section [12.1.3](#). Further details on the summary statistics of these questionnaires will be provided in the SAP.

#### 12.6.1.2 Product Acceptance

Product acceptance questionnaire will be described as detailed in section [12.1.3](#). Further details on the summary statistics of this questionnaire will be provided in the SAP.

#### 12.6.1.3 Product Use

Nicotine/tobacco containing product use will be derived from product use diary. Some further exploration based on BoExp levels could be added in the SAP. Product use and product use will be described as detailed in section [12.1.3](#).

#### 12.6.1.4 Biomarkers of Exposure

Biomarkers of Exposure (NEQ, total NNAL, and CEMA) will be described as detailed in section [12.1.3](#).

#### 12.6.1.5 CYP2A6

CYP2A6 will be described as detailed in section [12.1.3](#).

#### 12.6.1.6 ABOUT Dependence

Product Dependence Questionnaire will be described as detailed in section [12.1.3](#). Further details on the summary statistics of this questionnaire will be provided in the SAP.

#### 12.6.1.7 Product weighing

Amount of powder extracted from P3P during the PK assessment will be described as detailed in section [12.1.3](#). Further details will be provided in the SAP.

### 12.6.2 Statistical Analysis

An analysis of variance (ANOVA) will be conducted for Day 1 and Day 30 on VAS-craving endpoints in the linear scale following the same approach described in section 12.5.3 presenting LS Means and LS mean differences. Additional statistical analysis of secondary endpoints may be defined in the SAP.

### 12.6.3 Safety Endpoints

In general, all safety data will be listed and tabulated as described in section 12.1.3.

AE data will serve for the primary assessment of safety. Other safety variables monitored in this study include: incidence and frequency of P3P product events including malfunction/misuse; respiratory symptoms (cough assessment VAS and Likert scales); vital signs; spirometry; ECG data; clinical chemistry, hematology, and urine analysis safety panel; physical examination; concomitant medications.

The number and percentage of subjects with AEs, SAEs, and product events will be tabulated by system organ class and preferred term. Summaries will also be presented for AEs leading to discontinuation, AEs leading to death, AEs by relatedness to product exposure (with and without laboratory related AEs), AEs by severity, and laboratory AEs. Tabulations will be performed for both the number of subjects experiencing an event and the number of events.

Summary tables showing actual values and change from baseline of clinical findings will be provided for spirometry, ECGs, vital signs, and laboratory parameter. Descriptive statistics will be summarized by product variant and change from baseline will be presented for laboratory parameters, ECG, respiratory symptoms, and vital signs. Shift tables will be provided for selected laboratory, spirometry, and ECG data.

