## 8.4 Reporting of Other Events Critical to Safety Evaluations

### 8.4.1 Abnormal Results of Laboratory Tests

Any clinical safety laboratory test result that is outside of the normal reference range will be reviewed by the Investigator and assessed for clinical significance according to its severity. The severity of abnormal laboratory test result must be assessed using CTCAE version 4.03 grading scales ([Appendix C](#)). Whenever that grading scheme is not available for the laboratory result of concern, the Investigator should assess the severity and the clinical significance of that result using his/her medical judgment.

Abnormal laboratory test results detected at the Screening Visit whose CTCAE grades are 2 or higher or still are CTCAE grade 1 and deemed clinically significant are usually concomitant disease or a manifestation of one and must be recorded accordingly.

However, in some instances, they may be assessed as AEs (and therefore must be handled according to the directions in section [8.2](#)) or as manifestations of already reported AEs. This decision will require a careful assessment of the abnormal result within the clinical context on a case-by-case basis and will depend on the Investigator's medical judgment.

Abnormal laboratory test results detected after the Screening Visit whose CTCAE grades are 2 or higher or still are CTCAE grade 1 and deemed clinically significant must be either recorded as AEs (and handled according to the directions in section [8.2](#)) or linked to a concomitant disease or still to an already reported AE.

The principles for assessing and reporting abnormal laboratory test results, emerging after the Screening Visit, using CTCAE 4.03 grading scales are set up in [Table 4](#):

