**Table 4 Principles for assessing and reporting abnormal laboratory test results**

Grading	Clinically significant?	Is it a grade increase from previous results in study?§	Report?
Grade 1	No	Not applicable	No
Grade 1	Yes	No	No*
Grade 1	Yes	Yes	Yes, as AE or linked to an already reported AE
Grade 2 or higher	No/Yes	No	No*
Grade 2 or higher	No/Yes	Yes	Yes, as AE or linked to an already reported AE

\* in this situation, this abnormal lab test result is either a manifestation of a concomitant disease or of an already reported AE.

§ grade increase in this context means the value is higher than the one from the Screening Visit.

In general, laboratory values will be recorded as “increased <lab parameter>” or “decreased <lab parameter>” to ensure consistency of recording/coding.

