9 CHANGES FROM THE PROTOCOL SPECIFIED STATISTICAL ANALYSIS

The following changes with respect to the analysis populations were made in the SAP compared to the Protocol:

- Changes regarding Population of Subjects to be Used for Different Endpoints

Endpoints	Protocol	SAP
Pharmacodynamics (VAS craving, Sensory questionnaire, ABOUT™ -Product Experience)	PK	Randomized
Product Acceptance	PK	Randomized
Puffing Inhalation Behavior	PK	Randomized

In addition, results for the 2 variants combined will not be reported except for data collected at baseline.

- Changes regarding Analysis Model for PK and AUC for VAS craving score

In the protocol, an ANOVA model with sex and product exposure category as factors was anticipated to be used to compare PK parameters and AUC for VAS craving score between variants at Day 30. The ANOVA model was replaced by an ANCOVA model with sex and product exposure category as factors and Day 1 value as covariate.

No Day 1 comparisons will be performed. Within-group comparisons Day 30 versus Day 1 will also be performed in an ANOVA model with sex and product exposure category as factors.

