12 PLANNED STATISTICAL METHODS

12.1 General Considerations

Data analysis will be performed using SAS[®] Version 9.3 or higher.

Data listings will be provided for all data collected, ordered by P3P variant and subject, unless otherwise stated. Summary statistics and statistical analysis will only be presented for data where detailed in this SAP. All unscheduled assessments will be included in the listings only.

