If a subject has more than one occurrence of the same AE, the subject will be counted only once within a PT for each P3P variant, with the worst occurrence based on the presentation (e.g., for presentation by severity = most severe, for presentation by relationship = most related). Missing information on the intensity of AE will be counted as severe.

The data will be presented in the below outputs:

TFL number	Title
TABLES	
15.2.23.1	Summary of Adverse Events – Safety Population
15.2.23.2	Summary of Adverse Events by System Organ Class and Preferred Term – Safety Population
15.2.23.3	Summary of Adverse Events Related to Investigational Product by System Organ Class and Preferred Term - Safety Population
15.2.23.4	Summary of Adverse Events Related to Study Procedures by System Organ Class and Preferred Term - Safety Population
15.2.23.5	Summary of Expected Adverse Events by System Organ Class and Preferred Term
15.2.23.6	Summary of Adverse Events by System Organ Class, Preferred Term and Severity – Safety Population
15.2.23.7	Summary of Adverse Events Leading to Investigational Product Discontinuation by System Organ Class and Preferred Term – Safety Population
15.2.23.8	Summary of Adverse Events Leading to Study Discontinuation by System Organ Class and Preferred Term – Safety Population
LISTINGS	
15.1.23.1	Listing of Exposure Emergent Adverse Events
15.1.23.2	Enrolled but not started randomized product use AEs
15.1.23.3	Safety follow-up AEs
15.1.23.4	Listing of AEs leading to study discontinuation

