12.5.9.4 Clinical Laboratory Evaluation

Table 15 lists the hematology, clinical chemistry, and urine analysis parameters to be assessed in this study at Screening, Admission, Day 15, and Day 30.

Table 15: List of Laboratory Safety Parameters

Hematology	Clinical chemistry	Urine analysis
Hematocrit	Albumin	pH
Hemoglobin	Total protein	Bilirubin
Mean corpuscular hemoglobin	Alkaline phosphatase	Glucose
Mean corpuscular hemoglobin concentration	Alanine aminotransferase	Nitrite
Mean corpuscular volume	Aspartate aminotransferase	RBC traces
Platelet count	Blood urea nitrogen	Protein
Red blood cell (RBC) count	Creatinine	Specific gravity
White blood cell (WBC) count	Gamma-glutamyltransferase	
Differential WBC count:	Fasting glucose	
• Neutrophils	Lactate dehydrogenase	
• Basophils	Potassium	
• Eosinophils	Sodium	
• Lymphocytes	Total bilirubin	
• Monocytes	Direct bilirubin	
	Total cholesterol	
	Triglycerides	
	CRP (C-Reactive Protein)	

Any clinical safety laboratory test result that is outside of the normal reference range will be reviewed by the PI and assessed for clinical significance. If the PI considers the abnormal result to be of clinical significance, then it must be recorded as a concomitant disease at Screening, or if not present at Screening, as an AE during the study. If the condition worsens after screening it will be recorded as an AE. Abnormal laboratory test results detected at the Screening Visit whose Common Toxicity Criteria Adverse Event (CTCAE) grades are 2 or higher or still are CTCAE grade 1 and deemed clinically significant are usually concomitant disease or a manifestation of one and must be recorded accordingly. Abnormal laboratory test results detected after the Screening Visit whose CTCAE grades are 2 or higher or still are CTCAE grade 1 and deemed clinically significant must be either recorded as AEs or linked to a concomitant disease or still to an already reported AE.

The grading scheme used in the Common Terminology Criteria for Adverse Events and Common Toxicity Criteria [CTCAE] version 4.03) will be used by the PI to assess abnormal laboratory AEs.

Laboratory data will be summarized and listed at Screening, Day -1, Day 15 and at Day 30 or early termination, together with changes from baseline (last measurement obtained from screening or day -1 measurements). The number and percentage of subjects with:

- normal/low/high values

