13.3 Final Analyses

Final analyses for this study will be performed only after database lock. A pre-analysis data review meeting will be held prior to database lock and completion of the final analyses. In addition, no database may be locked, randomization code unblinded, or analyses completed until the final version of this SAP has been approved.

Any post-hoc, additional exploratory analyses completed to support planned study analyses, which were not identified in this SAP, will be documented and reported as applicable. Any results from these unplanned analyses will also be clearly identified in the text of the RSR.

The list of all tables, figures and listings to be presented are included in the relevant sections of the SAP.

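### The SAP omits, without declaring it, the related-AE summary without laboratory AEs and the laboratory-AE summary that protocol 12.6.3 requires

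*Protocol*

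**What the plan says.** Protocol 12.6.3 names the AE summaries to be produced. Among them are "AEs by relatedness to product exposure (with and without laboratory related AEs), AEs by severity, and laboratory AEs". The bracketed condition belongs to the relatedness summary, and laboratory AEs are a further item of their own.

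SAP 12.5.9.2 lists the AE outputs. The relatedness table appears once, as 15.2.23.3: "Summary of Adverse Events Related to Investigational Product by System Organ Class and Preferred Term - Safety Population". No table in the series excludes laboratory AEs or is restricted to them.

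Two SAP statements close the list. SAP 12.1: "Summary statistics and statistical analysis will only be presented for data where detailed in this SAP". SAP 13.3: "The list of all tables, figures and listings to be presented are included in the relevant sections of the SAP".

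SAP section 9 sets out departures from the protocol, beginning "The following changes with respect to the analysis populations were made in the SAP compared to the Protocol". It covers analysis populations, reporting of the two variants combined, and the models for PK and VAS craving. AE tables are not mentioned.

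On how a laboratory result becomes an AE, protocol 8.4.1 covers "Abnormal laboratory test results detected after the Screening Visit whose CTCAE grades are 2 or higher", together with grade 1 results judged clinically significant. SAP 12.5.9.4 repeats that such results "must be either recorded as AEs or linked to a concomitant disease or still to an already reported AE". Protocol Table 4 adds that the grade must have increased since Screening. For grade 2 or higher with an increase, its entry is "Yes, as AE or linked to an already reported AE", whatever the answer on clinical significance.

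**The concern.** The protocol committed to showing product-related AEs both ways and to showing laboratory AEs alone. The SAP drops both outputs without saying so, for the data that carry the main safety assessment.

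The split has a purpose in this trial. A laboratory result can become an AE through a grading rule, without any symptom and without being clinically significant. SAP 12.5.9.1 puts all AEs after the product test into the summary tables. The related-AE rate for an inhaled nicotine powder can therefore combine symptoms such as cough, nausea or dizziness with laboratory findings that the investigator judged related. A reader of the planned tables would see one percentage per variant and could not tell how much of it is symptomatic.

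**Working it through.** The documents state no AE or laboratory-AE rate, so there is no figure to reproduce. The check is mainly a comparison of texts.

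**1. Required against planned.**

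| Protocol 12.6.3 item | SAP output |
|---|---|
| Related AEs, laboratory AEs included | 15.2.23.3, and the related-AE row of 15.2.23.1 |
| Related AEs, laboratory AEs excluded | none |
| Laboratory AEs alone | none |
| AEs by severity | 15.2.23.6, and the severity rows of 15.2.23.1 |

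The topline set in SAP 13.2 takes Tables 15.2.23.1 and 15.2.23.2 from the same list and adds nothing. Tables 15.2.26.1 to 15.2.26.15 summarise laboratory values, grades, clinical interpretation and shifts. They do not summarise laboratory AEs.

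**2. How a laboratory result reaches the related-AE rate.** Four conditions must hold.
- The result is grade 2 or higher, or grade 1 and clinically significant, and the grade is above that at Screening (Table 4).
- It is recorded as a new AE, not linked to a concomitant disease or an existing AE (protocol 8.4.1).
- It falls after the product test. Day -1 safety bloods are drawn before it (protocol Table 6), so Day 15, Day 30 and early-termination samples are the main contributors.
- The investigator judges it related (protocol 8.2.4).

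**3. Whether the planned tables already contain the missing rate.** In one arm, let A be the number of subjects with any related AE and L the number with a related laboratory AE. The number with a related AE that is not a laboratory AE lies between A − L (every laboratory AE is the subject's only related AE) and A (none is). The tables do not say where in that range it falls. L itself is not tabulated either, because subjects may appear under several laboratory terms. A system organ class row cannot be assumed to equal laboratory AEs, since protocol 8.4.2 also turns clinically significant ECG, spirometry, vital-sign and body-weight findings into AEs.

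**4. What pooling can do to a difference between variants.** Let s be the proportion of subjects with a symptom AE and q the proportion with a laboratory AE, independent of each other within an arm. The pooled proportion is 1 − (1 − s)(1 − q). All rates below are assumptions for illustration.

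| Symptoms, two arms | Laboratory, two arms | Pooled | Difference, symptoms → pooled |
|---|---|---|---|
| 20% v 50% | 20% v 20% | 36% v 60% | 30 → 24 points |
| 20% v 50% | 30% v 10% | 44% v 55% | 30 → 11 points |
| 20% v 50% | 10% v 30% | 28% v 65% | 30 → 37 points |
| 30% v 30% | 10% v 30% | 37% v 51% | 0 → 14 points |

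First row: 1 − 0.8 × 0.8 = 0.36 and 1 − 0.5 × 0.8 = 0.60. With equal q in both arms the difference is multiplied by (1 − q). If laboratory AEs occur only in subjects who already have a symptom AE, independence fails and the subject-level rate does not change.

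**The case against.** The strongest reply is that little information is lost. Laboratory AEs are generally recorded with uniform terms for an increased or decreased parameter, so they show as separate preferred-term rows in 15.2.23.2, 15.2.23.3 and 15.2.23.6. Listing 15.1.23.1 gives subject-level AEs and is in the topline set; with 60 randomized subjects, those with only laboratory AEs can be counted by hand. Laboratory abnormalities are tabulated by grade and shift. Cough has its own tables, and dizziness and nausea form a questionnaire subscale. No between-variant test of AE rates is planned. All of this stands and limits the consequence. It does not supply the two promised outputs or explain their silent removal, and a hand count from a listing is not a planned summary.

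A reader might infer more than the documents support:
- *That every AE summary must be split.* The with-and-without condition in 12.6.3 attaches to relatedness only.
- *That pooling dilutes differences between variants.* This needs laboratory-AE rates that are equal across arms and independent of symptoms. The documents give no rates, and the third and fourth rows of the table above show the opposite effect.
- *That laboratory fluctuation fills the related-AE rate automatically.* Table 4 triggers reporting; relatedness needs a separate investigator judgement.
- *That several laboratory scales begin at grade 2.* In Tables C1 to C3 only lymphocyte increase does.

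**Conclusion.** The omission is established from the text alone: one version of the relatedness summary and one laboratory-AE summary are required by the protocol, absent from the SAP, excluded by the SAP's own limit on what is summarised, and undeclared in section 9.

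The effect on the results cannot be sized or given a direction. It depends on how many laboratory results become new AEs, how many of those are judged related, how they fall across variants, and how far they overlap with symptoms. The documents are silent on each. What can be said is that the related-AE rates may mix two kinds of event, and that the planned tables do not let a reader separate them per subject. That uncertainty is a reason to show both versions, as the protocol intended. It is not evidence that the planned rates are biased towards or against either variant.

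**What to change.** In SAP 12.5.9.2 add, by variant and overall:
- a version of Table 15.2.23.3 that excludes laboratory AEs;
- a table of laboratory AEs.

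Both need one flag that marks AEs raised under protocol 8.4.1. The rule should say how a result merely linked to an existing AE is treated. It should be fixed before database lock, because SAP 6.3.2 leaves sponsor and CRO personnel unblinded to variant.

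If the sponsor prefers not to produce these tables, SAP section 9 should declare the omission and give the reason.

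Rows excluding laboratory AEs for any AE and related AE in Table 15.2.23.1 would be a useful low-cost addition, but the protocol does not require them.

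Cost: one flag and two tables adapted from existing programs, with no new data collection.
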